8.5 Treatment Effect Analyses

Secondary Endpoint Analyses

Event counts over 60 days will be analyzed by Poisson regression as described above in 8.4. Time

to events will be analyzed by Cox regression. Differences between belnacasan and placebo with

respect to change in continuous endpoints will be assessed by mixed effects models for continuous

repeated measures data and mixed effects logistic models for repeated categorical variables.

Endpoint proportions of belnacasan and placebo groups will be assessed by contingency table

analysis (chi-square).

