 - o from randomization to the first day of achieving sustained (i.e., at least 2 days) resolution of fever for subjects who presented with fever at any point between enrollment and day 2 post randomization

- with temperature <38C or >=38C experienced in total during the first 28 days post randomization
- o from randomization to the first day post randomization of achieving oxygenation of SpO2>=96% in room air when resting for subjects who presented with SpO2>93% and <96% in room air, when resting, at enrollment
- o with oxygenation of SpO2>= 96% or SpO2>93% in room air, when resting, in total during the first 28 days post randomization

3. COVID-19 related deterioration and mortality

- **3a. Deterioration and mortality rates:** Proportion of treatment group, versus placebo group, respectively, who per subject reporting or medical records by day 14, day 28 and by day 60 post randomization had experienced:
 - o an emergency department visit, other than at study enrollment or study visits
 - hospitalization for COVID-19
 - o hospitalization for COVID-19 requiring oxygen
 - hospitalization for COVID-19 requiring ICU
 - o hospitalization for COVID-19 requiring ventilation
 - o COVID-19 related death
 - death
 - hospitalization or death
- **3b.** *Time to and length of deterioration*: Comparison of treatment group versus placebo group, respectively, in the number of days
 - o from randomization until the first day of experiencing hospitalization for COVID-19
 - o of hospitalization for COVID-19 experienced in total by day 14, by day 28 and by day 60 post randomization
 - o of hospitalization for COVID-19 requiring oxygen experienced in total by day 14, by day 28 and by day 60 post randomization
 - of hospitalization for COVID-19 requiring ICU experienced in total by day 14, by day 28 and by day 60 post randomization
 - o of hospitalization for COVID-19 requiring ventilation experienced in total by day 14, by day 28 and by day 60 post randomization

4. WHO 9-Point Ordinal Scale

- 0. Uninfected or "no clinical or virological evidence of infection"
 - a. defined as subject answering "Yes" to "In the past 24 hours, have you returned to your usual health (before your COVID-19 illness)?"
- 1. Not hospitalized, no limitations on activities
 - a. defined as subject answering "Yes" to "In the past 24 hours, have you returned to your usual activities (before your COVID-19 illness)?"
- 2. Not hospitalized, limitation on activities

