5.2 Study Assessments

Table 1: Schedule of Events: **1** = In-Person; **2** = Telephone; **3** = Subject Self-Tracking

Time Point (Days)	Screen / enroll	D19	D4	D7	D10	D14	D21	D28	D42	D60	ET ¹⁰
STUDY TEAM											
Inclusion / Exclusion	İ										
Consent	İ							\			
Screening Tests ^{1, 12}	İ					1					
Demographics	İ										
CXR or CT ¹³	İ										
Physical Exam	İ			İ		1	Ť	Ţ			ţ
Vitals ²	İ			İ		İ	İ	İ			İ
EKG	İ			İ		İ	İ	İ			İ
CoV-2 N/P ³	İ					İ		Ť			Ť
Standard labs ^{4, 12}	İ			İ		Ì		Ť			Ť
Blood draws ^{5, 12}	İ			İ		1	Ť	Ť			İ
Immunology tests ^{6, 12}	İ			İ		Ì	Ť	Ť			Ť
CoV-2 blood ^{7, 12}								Ť			Ť
AE assessment	İ	2	2	İ	2	Ţ	İ	Ī	2	~	Ĭ
Symptoms assessment	İ	2	2	İ	2	Ţ	İ	İ	2	~	İ
WHO 9-Point Scale ⁸	İ	2	2	İ	2	Ţ	İ	İ	2	2	İ

SUBJECTS (as recorded in study diary)						
IP/placebo intake	Three times per day through day 28 or ET					
Temperature ¹¹	Daily via thermometer through day 28 or ET; subject will report via telephone to					
	study team at Day 42 & 60					
SpO2 resting ¹¹	Daily via pulse oximeter through day 28 or ET; subject will report via telephone to					
	study team at Day 42 & 60					
Symptom tracking	legistrian One time per day through day 28 or ET; subject will report via telephone to study					
	team at Day 42 & 60					

¹Screening tests: HIV, Hepatitis B, Hepatitis C, and pregnancy (serum pregnancy test for women of child-bearing potential per MedStar definition at enrollment and at day 14).

²Vital signs: oral temperature, heart rate, systolic blood pressure.

³Quantitative nasopharyngeal SARS-CoV-2 RNA testing (RT-PCR): nasopharyngeal or throat swabs will be used; any FDA-approved or commercial testing method will be acceptable. A home health agency may be used to confirm COVID-19 by RT-PCR in the subjects' home in the event their initial testing did not include PCR, to ensure expeditious resulting and appropriate inclusion into the trial. If home health is used to collect the PCR test or there is a delay in PCR resulting at initial screening, the subject will return to either MedStar Washington Hospital Center or MedStar Franklin Square for completion of the screening/enrollment visit in 1 to 3 days, once positive PCR is confirmed, to complete all study procedures including randomization and medication dosing under observation. ⁴Standard labs: serum chemistry, coagulation tests and hematology. Pregnancy tests for women of childbearing potential at screening, day 14 and end of treatment.

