⁵Blood draws: serum and peripheral blood mononuclear cells for later immunological analysis.

- ⁹Day 1 (i.e., the first day of drug intake) is most likely also the screen / enroll day; subjects will receive a phone call from Study Team a few hours after first dose is taken to check up on how they are doing.
- ¹⁰ET: Subjects who prematurely discontinue study drug for any reason are asked to have an Early Termination (ET) visit the day the last study drug dose was taken.
- ¹¹ Subjects will be given a digital thermometer and portable pulse oximeter to record their temperature and oxygenation daily in the provided subject diary.
- ¹² These laboratory tests will be collected at a one-time blood draw at each visit, a total of 5 collections at the 5 visits (Screening, Day 7, Day 14, Day 21, and Day 28). The amount drawn at each timepoint is as follows: Screening visit (56 mL or 11 teaspoons), Day 7 (44 mL or 9 teaspoons), Day 14 (56 mL or 11 teaspoons), Day 21 (20 mL or 4 teaspoons), and Day 28 (48 mL or 10 teaspoons). The early termination visit would be in lieu of one of the in-person visits, it is not included in the total. Laboratory tests collected at the screening/enrollment visit may be collected by a home health agency in the subjects' home.

¹³Chest x-ray or CT of the chest will be completed as standard of care but not required for screening or randomization or enrollment

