Subjects may withdraw voluntarily from participation in the study at any time and for any reason. Subjects may also be withdrawn on the basis of the Investigator's clinical judgment. This study may be terminated at the discretion of MedStar Health or of any regulatory agency for reasons including safety and/or treatment effect.

For enrolled subjects we anticipate that the main reasons for discontinuation of therapy will be either withdrawal of consent for continuation in the study or inability to tolerate the study. Other instances may include patient death, inability to take the study drug from severity of illness or inhospital complexity of illness. Subjective intolerance of the drug from minor side effects or alternatively cessation of COVID-19 related symptoms well ahead of the 28-day schedule may cause patients to want to discontinue the drug. With regards to drug toxicity itself, we anticipate minor symptomatology from adverse effects, such as headache, dizziness, nausea and vomiting, abdominal discomfort and rash (see also 1.4) based on prior human trial experience with the study drug. Should any subject dosed on the study drug experience seizures, which was reported as an

unrelated adverse event in an epilepsy trial, that individual would be subject to discontinuation out of an abundance of caution. Any emergent symptom that has no clear cause will result in a hold on subsequent study drug dosing until protocol assessment by the Study Investigator. The reasons for discontinuation of study drug will be documented clearly. In all cases study protocol monitoring will continue for the entire 60 days of the protocol as long as the subject stays consented.

When a subject withdraws or is withdrawn before completing the study, the date and reason for withdrawal are to be documented. Subjects who withdraw or who are withdrawn prematurely are to attend an early termination, at which time they will complete all assessments as outlined in the Schedule of Events (Table 1); moreover they will be encouraged to stay enrolled so that further safety and outcome information can be collected and analyzed.

In the event that a subject is withdrawn prematurely due to an adverse event or serious adverse event, the adverse event or serious adverse event will be followed until it resolves or stabilizes, or until it is judged by the Investigator to be no longer clinically significant.

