8.4 Safety & Tolerability Analyses

All safety & tolerability analyses will be performed on the Safety Population. The safety data will be presented in individual listings and summary tables.

Overall safety will be assessed by the number of belnacasan VX-765/RVT-201/MSR-001 dosed subjects experiencing a grade 4 or 5 SAE during the trial. Of 20 subjects enrolled in the belnacasan group, 3 or more developing a grade 4 or 5 SAE probably related to belnacasan would be

considered unlikely due to chance. Therefore, belnacasan will be determined safe if no more than

2 subjects develop a grade 4 or 5 SAE in the belnacasan group probably related to belnacasan.

In terms of stopping rules, should two or more subjects develop a similar Grade 3 SAE that is at

least possibly related to belnacasan or should one or more subjects develop a \geq Grade 4 SAE that

is at least possibly related to belnacasan, the trial will be paused for DSMB safety review.

Primary Endpoint Analysis

Primary endpoints of adverse and serious adverse events (AE/SAE) will be assessed by Poisson

regression for count data. Events will be counted out to 60 days from randomization to belnacasan

or placebo groups. Because some subjects may be followed for less than 60 days, subject follow-

up time will be included in the Poisson regression as the exposure time variable. If counts are not

Poisson-distributed, either over- or under-dispersed, negative binomial regression will be to

analyze AE/SAE events with appropriate adjustment for over/under dispersion. Comparison of

belnacasan vs. placebo will be expressed as the incidence rate ratio (IRR).

Adverse Events

AEs will be coded according to the latest version of the Medical Dictionary for Regulatory

Activities (MedDRA). The intensity/severity of AEs will be graded according to NCI-CTCAE (see

Section 7.3).

TEAEs, AEs leading to study treatment discontinuation, AEs leading to dose interruption, AEs

related to study medication, SAEs, and AEs leading to death will be summarized by system organ

class, preferred term, and study period. A summary of AEs that are CTCAE Grade 3 or higher, as

well as the most frequent preferred terms, will be provided.

If a subject experiences the same adverse events multiple times within a period, then the event will

be counted only once within the period and by greatest severity.

Descriptive statistics will be used to summarize the safety data.

Clinical Laboratory Values

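### On the most natural reading of the plan, a missing diary day counts as a day without the condition in the 2b fever and SpO2 day totals

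*Combined protocol and SAP*

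**What the plan says.** **Endpoint.** Section 3.4, item 2b, compares the number of days "with temperature <38C or >=38C experienced in total during the first 28 days post randomization" and the number "with oxygenation of SpO2>= 96% or SpO2>93% in room air, when resting, in total during the first 28 days post randomization". Each is one total per subject over a fixed 28-day window.

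**Data source.** A footnote to Table 1 in 5.2 states: "Subjects will be given a digital thermometer and portable pulse oximeter to record their temperature and oxygenation daily in the provided subject diary". Table 1 gives the collection window for temperature as "Daily via thermometer through day 28 or ET", and the SpO2 row has the same limit. Section 7.2, by contrast, tells subjects who stop study drug to go on completing the diary and attending visits.

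**Follow-up.** Under 5.3, monitoring after drug discontinuation runs to day 60 while consent stands. A subject who stops drug is therefore not a dropout.

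**Analysis.** Section 8.2 gives counts to Poisson regression. Section 8.5 says "Event counts over 60 days will be analyzed by Poisson regression as described above in 8.4". In 8.4 the exposure is subject follow-"up time will be included in the Poisson regression as the exposure time variable". No other exposure is defined.

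**Missing data.** Section 8.6 expects missing values and will examine their pattern. For Poisson models it says only that data are used up to dropout. It has no rule for a diary day missed while the subject is still being followed.

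**The concern.** A 2b day can be counted only if the diary holds a reading for it. If the exposure is follow-up time, a day with no reading adds one day to the denominator and nothing to the numerator, whichever condition is being counted. The endpoint's own structure shows the fault. Days <38C and days >=38C are complementary, yet one missing day lowers both totals.

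An arm with more missing diary days would then show fewer fever days, which looks better, and fewer good-oxygen days, which looks worse, with no true difference. Unequal missingness is plausible. Section 5.3 expects some subjects to stop for intolerance, and says that "cessation of COVID-19 related symptoms well ahead of the 28-day schedule may cause patients to want to discontinue the drug". Either reason could differ by arm. The negative binomial fallback in 8.4 does not help, because it changes the variance and leaves the exposure as it is.

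The secondary objective is to estimate effect sizes, and 8.7 says that the estimate will inform a larger trial. A ratio that partly measures diary completion weakens that output.

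**Working it through.** The plan gives no figure for this point. Its one design figure, the rate-ratio difference of over 60% in 8.7, does not bear on it and cannot be reproduced uniquely because no baseline rate is stated.

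**Inputs.** From the documents: a 28-day window (3.4, 2b), one reading per day (5.2), exposure equal to follow-up time (8.4) and 20 subjects per arm (8.7). Assumed, because the documents give none: the share of subjects who stop the diary early, the day on which they stop, and the share of diary days skipped.

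**1. One subject.** Take 6 fever days and 22 afebrile days in 28, with 20% of diary days missing at random.
- Fever days recorded: 6 × 0.8 = 4.8, and 4.8/28 = 0.171 per day. The truth is 6/28 = 0.214.
- Afebrile days recorded: 22 × 0.8 = 17.6, and 17.6/28 = 0.629. The truth is 22/28 = 0.786.
- The two rates sum to 0.80, so a fifth of the window counts as neither febrile nor afebrile.

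**2. Early diary stopping, no true effect.** Suppose a fraction d of an arm stops the diary at day 7 but stays in follow-up, and the daily chance of SpO2 >=96% is constant and equal in both arms. Mean recorded days are (1 − d) × 28 + d × 7. The daily chance cancels, so the rate ratio is the ratio of recorded days.

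| Stop at day 7 (belnacasan / placebo) | Mean recorded days | Rate ratio |
|---|---|---|
| 25% / 5% | 22.75 / 26.95 | 0.844 |
| 15% / 5% | 24.85 / 26.95 | 0.922 |
| 20% / 10% | 23.80 / 25.90 | 0.919 |
| equal | equal | 1.00 |

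**3. Scattered skipped days, no true effect.** With fractions mT (belnacasan) and mC (placebo) missing, the ratio is (1 − mT)/(1 − mC).
- 20%/20%: 1.00
- 20%/10%: 0.8/0.9 = 0.89
- 30%/10%: 0.7/0.9 = 0.78
- 10%/30%: 0.9/0.7 = 1.29

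A simulation of SpO2 days used 2,000 trials, 20 subjects per arm, a subject-level daily probability drawn from Beta(8,2), and a two-sided 5% Wald test. With follow-up exposure it rejected the null in 0.03 of trials at 20%/20%, 0.36 at 20%/10% and 0.94 at 30%/10%. With recorded days as exposure it rejected in about 0.01 each time.

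**4. Is recorded days as exposure a sufficient repair?** No. The simulation favours it only because missingness there is unrelated to the day's state.
- *Fever.* Take the 25%/5% case and give every subject 3 fever days, all by day 7. A 28-day exposure gives (3/28)/(3/28) = 1.00, which is correct. Recorded days give (3/22.75)/(3/26.95) = 1.18, a false excess on belnacasan.
- *Oxygen.* Suppose a subject is at >=96% on days 1–7 and on supplemental oxygen on days 8–28. With only room-air readings counted, the score is 7/7; over the full window it is 7/28. The deterioration disappears.

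**The case against.** **The model for 2b is inferred.** This stands. The sentence in 8.5 speaks of 60 days while 2b covers 28, and the exposure in 8.4 is written for adverse event counts. Section 8.5 also lists mixed effects logistic models for repeated categorical variables. Applied to daily fever or SpO2 status, that model gives a missing day no weight. Poisson remains the more natural reading because 2b is worded as a total per subject and 8.2 sends counts there. A reader might infer that the plan states that a missing day is a day without the condition. It does not; that follows from the exposure definition and the absence of any other rule.

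**Diaries may not stop with the drug.** Section 7.2 asks for them to continue, while Table 1 ends them at early termination. The documents therefore do not establish that every subject who stops drug loses later readings. Reminders (5.1) and weekly diary collection also limit gaps. Neither settles the conflict, and neither says how a skipped day is handled.

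**The follow-up to day 60.** A reader might infer that the extra 60 − 28 = 32 days of exposure bias the comparison. When both arms are followed alike, those days are the same in each and cancel from the ratio.

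**The size is assumed, and the trial is exploratory.** Both are true. Equal missingness lowers the rates but leaves the ratio at 1.00.

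**Conclusion.** The concern holds as a gap in specification with a predictable bias. On the most natural reading of 8.2, 8.4 and 8.5, a diary day missed during follow-up counts against whichever 2b condition is being totalled. If missingness differs by arm, the ratio for SpO2 >=96% days is about 0.84 at 25%/5% stopping at day 7, and about 0.92 at 15%/5% or 20%/10%, with no true effect. Those figures rest on assumed stopping rates and a constant daily probability. For fever that falls early, the bias from late diary stopping is smaller, and it is nil in the example above.

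The documents do not show that the bias will occur. That needs unequal missingness, for which they give no rate. The affected items are secondary and the primary safety endpoint is not touched. The point should still be settled before unblinding, because the remedy is cheap and effect sizes are the purpose of these endpoints.

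**What to change.** 1. State in 8.5 that the 2b day totals are compared over days 1–28 with the mixed effects logistic model for repeated categorical data already listed there, applied to daily status with study day in the model. A missing day then contributes nothing, and modelling study day keeps early-falling fever from being distorted by early diary stopping.
2. Count days on supplemental oxygen as not meeting the room-air SpO2 condition, and do not drop them.
3. Report the number of recorded days by arm.
4. Add a sensitivity analysis, because stopping after recovery or intolerance may be informative.
5. Reconcile Table 1 with 7.2 on whether the diary continues after study drug stops.

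The cost is a few sentences in the analysis section, a daily status variable and slightly more analysis work. The model yields odds ratios; expected days per arm can be recovered by summing fitted daily probabilities over days 1–28. It still assumes that missingness is explained by the observed data, which is why item 4 is needed.

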 - a. defined as subject answering "No" to "In the past 24 hours, have you returned to your usual activities (before your COVID-19 illness)?"
- 3. Hospitalized, not requiring supplemental oxygen
- 4. Hospitalized, requiring supplemental oxygen
- 5. Hospitalized, on non-invasive ventilation or high flow oxygen devices
- 6. Hospitalized, intubated
- 7. Hospitalized, advanced life support including invasive mechanical ventilation or ECMO
- 8. Death
- **4a)** Ordinal scale rates: proportion of treatment group versus placebo group, respectively who had experienced:
 - o an improvement from scale 2 at randomization to scale 1 or 0 on days 4, 7, 10, 14, 21, 28, 42, 60 post randomization,
 - o an improvement from scale 1 at randomization to scale 0 on days 4, 7, 10, 14, 21, 28, 42, 60 post randomization
 - o a sustainment from scale 1 at randomization to scale 1 on days 4, 7, 10, 14, 21, 28, 42, 60 post randomization
 - o any improvement of the scale (i.e., at least a 1-point decrease) between enrollment and days 7, 14, 28, 42, 60 post randomization
 - any worsening of the scale (i.e., at least a 1-point increase) between enrollment and days 7,
 14, 28, 42, 60 post randomization
 - o scale 4 or higher by day 28 or day 60 post randomization
 - o scale 6 or higher by day 28 or day 60 post randomization

- *4b) Ordinal scale averages, highs, and lows:* Comparison of treatment group versus placebo group, respectively, at days 14, 28 and 60 post randomization in the
 - o average of daily scale value on that day
 - o overall average of daily scale value experienced since enrollment
 - o in the worst (i.e., highest) daily scale value experienced since enrollment
 - o in the best (i.e., lowest) daily scale value experienced since enrollment
- **4c)** Time to improvement: Comparison of treatment group versus placebo group, respectively, in the number of days from enrollment until first experiencing a 1-point improvement sustained over at least 2 days by day 14, day 28 and by day 60 post randomization
- *4d) Length of ordinal scale experience:* Comparison of treatment group versus placebo group, respectively, in the total number of days by day 14, day 28 and by day 60 post randomization on which subjects experienced a given scale value (i.e., 3, 4, 5, 6, 7)

5. Surrogate markers of COVID-19-related inflammation and organ involvement

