8.2 Analysis Methods

General Methods

FDA Data Standard Guidelines will be followed. Continuous variables will be summarized using the number of observations, number of observations above the limit of quantification (if applicable), mean, standard deviation (SD) median, and range. Categorical variables will be summarized using frequency counts and percentages. Comparison of belnacasan (VX-765/RVT-201/MSR-001) and placebo groups will utilize Poisson regression for counts, Cox proportional hazards regression for time-to-event data and mixed effects models for continuous and categorical data obtained over study days.

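### No model is named for the total-day endpoints (2b, 3b, 4d); the nearest stated route, Poisson with a negative binomial fallback, misstates their precision in several plausible cases

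*Combined protocol and SAP*

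**What the plan says.** Three groups of secondary endpoints in Section 3.4 are one total of days per subject.

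- 2b: days "with temperature <38C or >=38C experienced in total during the first 28 days post randomization", and days "with oxygenation of SpO2>= 96% or SpO2>93% in room air, when resting, in total during the first 28 days post randomization". The maximum is 28.
- 3b: days "of hospitalization for COVID-19 experienced in total by day 14, by day 28 and by day 60 post randomization", and the same for stays needing oxygen, ICU or ventilation.
- 4d: the "total number of days by day 14, day 28 and by day 60 post randomization" spent at each scale value from 3 to 7.

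On models, Section 8.2 states that comparison of the belnacasan and "placebo groups will utilize Poisson regression for counts". Section 8.5 adds: "Event counts over 60 days will be analyzed by Poisson regression as described above in 8.4". Section 8.4 continues: "If counts are not Poisson-distributed, either over- or under-dispersed, negative binomial regression will be to" analyse AE/SAE events (a verb is missing in the source), and promises a suitable dispersion adjustment without naming one. The other routes in 8.5 are Cox regression for times to event, mixed models for change in continuous measures and for repeated categorical measures, and chi-square for proportions. None of these sections mentions total days.

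**The concern.** Someone coding the analysis from Section 8 has no instruction for these totals. Each is a whole number per subject, and no route except the one for counts fits a single total per subject. Poisson regression assumes that the variance of the total equals its mean. Days in hospital come in blocks and many subjects will have none, so the variance should be well above the mean. Days below 38C or with SpO2 above 93% will often be close to 28, so the variance can be well below the mean. Section 8.4 offers negative binomial for both situations, but that model can only add variance to a Poisson.

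The secondary objective (Section 3.3) is to estimate effect size, and Section 8.7 says that the estimate will inform a larger trial. An interval much too narrow or too wide would mislead that planning.

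**Working it through.** **The plan's own figure.** None is given for total days. The only precision figure is in Section 8.7: a difference in rate ratios over 60% for 80% power, alpha 5%, 20 per arm. With Poisson, SE(log ratio) = sqrt[(1 + 1/RR)/(20 x control rate)]. For RR 0.4 and 1.636 control events per subject, SE = sqrt(3.5/32.72) = 0.327 and |ln 0.4|/SE = 0.916/0.327 = 2.80; 2.80 - 1.96 = 0.84, which is 80% power. The plan states no base rate, so the figure can be matched but not uniquely reproduced. It says nothing on dispersion.

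**Inputs.** From the documents: 20 per arm, alpha 5% (taken as two-sided), windows of 14, 28 and 60 days. Everything on rates, stay lengths and spread is assumed, because the documents give none.

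**Formulae.** Let m be the mean and f the variance/mean ratio.

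- Poisson SE of the log ratio with equal means: sqrt[2/(20m)]. The correct SE is about sqrt(f) times this.
- Poisson rejection rate under no effect: about 2 x [1 - Phi(1.96/sqrt(f))].
- Negative binomial variance: m + a x m^2 with a >= 0, so never below m. If f < 1 the fit collapses to Poisson.
- Beta-binomial days out of 28 with mean share p and within-subject correlation r: f = (1 - p)(1 + 27r).

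**Numbers put in.**

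- Hospital days, f = 13.38: 1.96/3.66 = 0.536, rejection about 59% (simulated 58%).
- SpO2 days, p = 0.7, r = 0.6: f = 0.3 x 17.2 = 5.16, rejection about 39% (simulated 38%).
- Days below 38C, mean 26, f = 0.19: Poisson SE = sqrt(2/520) = 0.062; simulated true SE 0.028; ratio 2.2. At means of 27 and 24 the ratios are 0.061/0.018 = 3.4 and 0.065/0.043 = 1.5.
- f falls below 1 when p > 1 - 1/(1 + 27r). That is a mean above 20.4, 24.9 or 26.4 days out of 28 for r = 0.1, 0.3 or 0.6.

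**Simulation under no effect** (4,000 trials per scenario, Wald tests, nominal 5%; trials with no estimable ratio excluded):

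| Assumed total | Variance/mean | Poisson rejects | Negative binomial rejects |
|---|---|---|---|
| Hospital days, 20-30% admitted, mean stay 4 or 8 | 5.8-13.4 | 40-58% | 4.7-5.7% |
| Hospital days, 5-10% admitted | 6.6-14.6 | 23-54% | 0.6-3.5% |
| Days >=38C, mean 1-4 | 2.5 | 20-22% | 6.1-7.0% |
| Days <38C, mean 24-27 | 0.09-0.42 | 0.0-0.4% | 0.0-0.4% |
| SpO2 days, r 0.1-0.3, share 0.30-0.85, variance above mean | 1.1-6.4 | 5-45% | 3.4-5.5% |
| SpO2 days, r 0.6, share 0.30-0.85 | 2.6-12.1 | 22-57% | 0.7-1.8% |
| SpO2 days, share 0.95 | 0.19-0.86 | 0-4.4% | 0-1.0% |

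At 5-10% admitted, 22-59% of trials had an arm with no hospital days, hence no rate ratio.

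**Shape at one mean.** SpO2 days with mean 18.7, from U-shaped to single-peaked, Beta(0.3, 0.15), (0.5, 0.25), (1, 0.5), (2, 1). In 1,500 trials each, Poisson rejects 48%, 40%, 33%, 21% and negative binomial 0.7%, 1.0%, 2.5%, 3.3%. A permutation test of mean days stays at 4-5%. At Beta(4, 2), (6, 3) and (8, 4), 1,200 trials each, negative binomial rejects 5.8%, 5.7% and 5.5%.

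**Power** (1,000 trials each). Afebrile days 27 v 25: 6% under either count model, 79% by permutation; 27 v 24: 45% v 97%. U-shaped SpO2 days 22.4 v 14: negative binomial 51%, permutation 75%.

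**The case against.** **Routing.** Section 8.5 speaks of event counts over 60 days. Total days are arguably not event counts, the 2b totals run over 28 days, and the fallback sentence names only AE/SAE events. A reader might infer that the plan expressly assigns these endpoints to Poisson; it does not. This stands, and the point is worded accordingly. If the sponsor did not mean Poisson, the endpoints have no model at all, and 8.5 needs a sentence either way.

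**Negative binomial works in many cases.** A reader might conclude that both models are always wrong. Clustering of days within a subject appears as over-dispersion of that subject's total, which negative binomial is built to absorb. It is close to nominal for moderately over-dispersed SpO2 days and for hospital days at 20-30% admitted, and slightly liberal for febrile days. This stands.

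**Poisson does not always produce false effects.** Near the ceiling it errs the other way. This stands too. The 28-day cap on every window also belongs to 2b alone; 3b and 4d extend to day 60.

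**The adjustment clause in 8.4.** It could be read as covering under-dispersion, but it names no method and is attached to a model that cannot express it.

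**Few admissions.** Section 5.1 regards admission as possible but not likely. With rare admissions a permutation test is as conservative as negative binomial (0-0.9% rejection), so a new test gains estimability there, not power. This limits what the fix can promise.

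**Conclusion.** The point holds in limited form. The plan names no model for total days, and the nearest stated route misstates precision in cases that the design makes plausible.

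- Plain Poisson intervals are far too narrow for hospital days and widely spread SpO2 days.
- They are too wide for totals near the 28-day ceiling (days below 38C, and SpO2 above 93% where most days qualify). Negative binomial changes little or nothing there.
- Negative binomial largely repairs moderate over-dispersion, but is too conservative for strongly U-shaped 28-day totals.
- With few admissions the rate ratio is often not estimable.
- Offering negative binomial for under-dispersion in 8.4 is an error on the face of the text, whatever the data look like.

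The sizes rest on assumed distributions; the direction of each error follows from the variance formulae. A reader might take this as a threat to the trial's main conclusion. It is not: the endpoints are secondary in a hypothesis-generating trial, and the primary AE/SAE comparison is a separate analysis. What suffers is the effect-size intervals passed to the next trial.

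**What to change.** In Section 8.5, name the total-day endpoints of 2b, 3b and 4d and take them out of the Poisson/negative binomial rule. For each:

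- Report the between-arm difference in mean days over its fixed window (28 days for 2b; 14, 28 and 60 days for 3b and 4d).
- Give a permutation p-value and a 95% interval consistent with it, either by inverting the permutation test or by a bootstrap with a small-sample correction. The plain percentile bootstrap runs slightly narrow at 20 per arm: it excluded a true zero in 6.3-6.8% of SpO2 trials and 7.1-8.3% of hospital-day trials at 20-30% admitted.
- For subjects with an incomplete window, use days per day observed.
- Where few subjects are admitted, give descriptive counts only.

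In Section 8.4, keep Poisson with negative binomial for AE/SAE counts, but delete under-dispersion as a reason to switch to negative binomial.

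The cost is a few lines of SAP text and code. The downside is that the follow-up offset of the regression is lost, which is why incomplete windows need the per-day-observed version.
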